1. Are the outcomes of the trial affected by alternative definitions of successful quitting and/or assumptions made about the status of missing cases?
2. If the strategies work, is this by reducing slip-ups and/or by enhancing recovery from slips, including short term relapse, or by some combination of the two? (EMA/qualitative sub studies complementing reports at follow-ups)
3. What, if any, sustained reductions in cigarette consumption occur (particularly reductions to non-daily use), among treatment failures and does this relate to any coping strategy?
4. What is the cost-effectiveness of any effective strategies, and does this differ between countries?
5. Do the strategies have different effects on people from different socioeconomic and ethnic groups, of different gender, with different prior smoking habits, and those who stopped smoking using different forms of medication?
6. How feasible and acceptable are the strategies to participants, and what are the barriers and facilitators to sustained cessation during the trial period? How are the relapse prevention strategies used, and are patterns of use related to cessation outcomes?
7. What are the rates of negative aspects (adverse events) reported in people who use a smoking replacement product compared to those who do not and does this vary by type of product used?

Curtailed Trial

Due to the small sample size and, hence, limited power, it will only be possible to assess the following objectives.

1. Are the outcomes of the trial affected by alternative definitions of successful quitting and/or assumptions made about the status of missing cases?
2. Do the strategies reduce slip-ups and/or enhance recovery from slips, including short term relapse, or by some combination of the two? (Explorative analyses of EMA/qualitative sub study data complementing lapse/relapse reports at follow-ups; e.g. EMA data will be used to calculate the frequency of self-reported slips by treatment group. Furthermore, multilevel models will be use to compare daily level of craving and withdrawal across groups overtime).

3. What, if any, sustained reductions in cigarette consumption occur (particularly reductions to non-daily use), among treatment failures and does this relate to any coping strategy? (Explorative analyses of EMA/qualitative sub study data complementing reduction reports at follow-ups; quantitative analysis will not be possible in the curtailed trial.)

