1a. Sensitivity analyses using different criteria to define abstinence, e.g. Russel Standard, defined as not smoking more than 5 cigarettes since 2-weeks post quit date. Sensitivity analyses using different approaches to imputed missing smoking status at 6 months; specifically, multiple imputation by chained equation and complete case analysis

1b: Point prevalence abstinence at 3- and 6-months, defined as no smoking (not even a puff) in the past seven days.

1c. Sustained reduction in cigarette consumption, defined as at least 50% reduction in cigarettes smoked per day (or week if originally non-daily smoker) from baseline in those who do not achieve abstinence at 6 months.

2. Evaluations of likely mechanisms of effect in particular focusing on these strategies that were encouraged and participant perceptions of effect (e.g. participant ratings), including use of explorative EMA/qualitative sub studies, e.g. using the EMA data, we will compare the characteristics of lapses across the four groups. Using multilevel models, characteristics of smoking lapses (triggers, levels of craving and withdrawal etc.) will be compared across the four treatment groups.

3. Rates of adverse events/serious adverse events (using MedDRA terminology) reported in people who use a smoking replacement product compared to those who do not and by type of product used.

Qualitative sub study

Original trial

At 3, 6- and 12-months post QD a sub sample of participants who had relapsed, lapsed, or remained abstinent will be invited to take part in a qualitative interview (N=160 in total, split equally between the 2 countries and 4 arms).

Curtailed trial

The qualitative study will provide data on the likely mechanisms of effect from ~100 participants who have and have not relapsed, and including lapsers, in the control and intervention arms from both countries, at 3 and 6 months. The following concepts will be looked at:

1. Feasibility, acceptability, use and perceived impact of study processes and interventions
2. How do lapses influence relapse?
3. Barriers and facilitators to maintaining abstinence
4. Cross-cultural perspectives, between UK and Australia, on cessation and relapse prevention support

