- Users of the SSS in the UK and the Quitline in Australia who are abstinent in the last 2 weeks of treatment (treatment period is typically 4 weeks post QD) and are still abstinent at point of recruitment. Additionally, in Australia, ethics permission was secured to recruit those quit between 7 and 100 days, and recruit from two additional sources: social media (via Facebook advertising) and St Vincent's Hospital, Melbourne.
- Willing to use a smoking replacement product or online behavioural support tool if allocated to use
- Aged 18 years and older
- Own a mobile phone
- Has Internet access
- Able to read/write/understand English

Exclusion Criteria

[figure not shown]
- Enrolled in other smoking cessation/relapse prevention research
- Currently using EC/oral NRT and planning to use for longer than 3 months

Study Design

[figure not shown]
This is a factorial randomised controlled trial with two comparisons added to usual care (UC; UC is generally 8-12 weeks of pharmacotherapy (e.g. varenicline or NRT), plus standard counselling provided from the commencement of the quit attempt), augmented by a series of text messages available in all conditions. Participants will be individually randomised to one of four arms: UC (Usual Care), SR (Smoking Replacement), S3P (Structured Planning and Prompting Protocol), or SR plus S3P.

Study Scheme Diagram

The study scheme below outlines the flow of participants through the trial and key time points for the original trial and curtailed trial.

Curtailed trial

Randomisation Procedures

Participants were randomised (stratified by country in permuted blocks of random size) to one of four study arms described in the Schedule of Intervention below. The randomisation ratio was 1:1:1:1 across the 4 study arms. Randomisation was done automatically via Stata code with the results imported into the web based program (Quest Engage) that directed the baseline study questionnaire, and occurred after all key baseline information was collected. The 4 arms are described as follows:

- 1. UC arm (control group, receives neither intervention):** If used as part of UC, this group will be encouraged to continue use of base medication (e.g. varenicline or patch) until the end of the recommended period of use.

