- Demographic details, smoking measures (e.g. heaviness of smoking index referenced to when they were smoking [21] information regarding previous quit attempts) and medical history (e.g. screening for depression, measures of perceived stress and affect)
- Information regarding the current quit attempt (including type of support/medicines used), frequency and strength of cravings, extent of slipups if any, plans on how long to continue use of base medication, self-efficacy for maintenance, perceived challenges, number of smokers in social network

All follow ups:

- Self-reported smoking status and cigarette consumption
- Detailed lapse/relapse report for those relapsing (e.g. no. of lapses, when, where, reasons, how many cigarettes at first lapse, how soon after first cigarette was full relapse)
- Strategies used to prevent relapse
- Cravings to smoke
- Participants who stop using SR/S3P/UC will be asked their reasons for doing so (if using at previous survey).
- Use of any, including non-allocated, smoking cessation/relapse prevention treatments
- Detailed use of SR/S3P/UC and ratings of the interventions, including helpfulness (3 month only) and adverse events.

12-month follow up additions – not available in the curtailed trial:

Saliva sample collection for those abstinent at 12 months. Cut off for abstinence is cotinine < 15 ng/ml [22] for those not reporting using any nicotine product and anabasine < 1 ng/ml [23] for those reporting other forms of nicotine use

- European Quality of Life-5 Dimensions (EQ5D) questionnaire
- Health Service Use Questionnaire
- Consumption of alcohol (binge drinking), including changes in consumption [24]).

Routinely collected data:

Use of the S3P will be collected by capturing data on the number of log-ins, number of assessments completed and number of text messages received.

Original Sample Size

We expect 70% of participants to relapse between 1-12 months in UC [25], and that each RP intervention will reduce the rate to 58%, and to 48% in those receiving both. Under these assumptions and comparing those who receive (2 arms) and do not receive (2 arms) each intervention individually, 257 participants are needed

per arm to detect a difference with 90% power ($\alpha=0.025$). We planned to recruit 350 in each arm, for the primary analysis, maximizing power, but retaining sufficient power if there is evidence that participation in the EMA study may have affected outcomes and these participants need to be excluded.

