Curtailed Trial Sample Size

The analysis plan is for the curtailed trial. The study was originally powered to be able to assess the effectiveness of the SR and S3P interventions (main effects); SR (2 arms) vs. no SR (2 arms) & S3P (2 arms) vs. no S3P with power = .90 and $\alpha = 0.025$.

With a final sample size of 235 and using $\alpha 0.025$, we have 30% power to detect a difference between arms (i.e. S3P vs no S3P or SR vs no SR), if one really exists. If we wanted to compare the 4 arms simultaneously in 1 model, the analysis would have 51% power with $\alpha 0.05$ (one-sided).

An alternative approach is to consider the study arms as an ordinal measure where participants are allocated to 0 (UC), 1 (S3P or SR arm), or 2 interventions (S3P+SR). We can assess whether the number of interventions received affects continued abstinence. With a final sample size of 235 and $\alpha = 0.05$ one-sided we have 78% power and this would also avoid multiple testing. We expect the intervention to be more effective at 12 months and, therefore, this is an optimistic power estimate but we can't estimate to what degree.

Overall, the latter approach offers us a viable option to explore differences in therapy on smoking relapse. The revised analyses for the curtailed trial will be useful for future meta-analysis looking at the impact of smoking replacement and/or Structured Planning and Prompting Protocol (S3P) on relapse.

ANALYSIS PLAN

Descriptive statistics

Participants' characteristics at baseline and follow-up will be presented broken down by all 4 arms using appropriate descriptive statistics; mean and standard deviation for continuous measures that are approximately symmetric; median and quartiles if they are skewed distributions. Discrete outcomes should be described using both the number and proportion (percentage). Similarly, summary measures of the primary (i.e. quit rates) and secondary outcomes by arms will also be presented.

Analysis of primary and secondary outcomes

Analyses for the primary and secondary outcomes will use the intention-to-treat (ITT) approach. All participants will be included in the analysis and will be analysed according to the treatment group to which they were randomised. All participants with missing outcomes at six months will be considered to be smoking (relapsed) as per Russell Standard, and to have not reduced their number of cigarettes smoked per day from baseline.

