
Point prevalence abstinence at 6 months, defined as no smoking (not even a puff) in the past seven days
	
6 month survey:
 
Have you smoked at all since we last surveyed you on <inset date>?
 
 1. No, not even a puff 2. Yes – just a few puffs 3. Yes – 1- 5 cigarettes in total 4. Yes – more than 5 cigarettes in total 
6 month survey:
 
When did you last smoke a cigarette?
 
 1. Today 2. Yesterday 3. 2-6 days ago 4. 1-2 weeks ago 5. More than 2 weeks to 30 days (1 month) ago 6. More than 1 month ago

Sustained reduction in cigarette smoking at 6 months in those who do not achieve abstinence. Defined as a 50% (or greater) reduction in cigarettes smoked (either per day or per week) at from baseline to 6 months post quit
	
6 month survey:
 
How many cigarettes do you currently smoke per day (OR per week if nondaily smoker)

6 month sustained abstinence according to the Russel standard, defined as smoking no more than 5 cigarettes since 2 weeks post target quit date
	
Baseline survey:
 
Have you smoked as much as a puff of a cigarette since you quit?
 
 1. No, not even a puff 2. Yes – just a few puffs 3. Yes – 1- 5 cigarettes in total 4. Yes – more than 5 cigarettes in total 
When did you last smoke?
 
 1. Earlier today 2. Yesterday 3. 2-3 days ago 4. 4-7 days ago 5. 8-14 days ago 6. More than 2 weeks ago 
3 and 6 month survey:
 
Have you smoked at all since we last surveyed you on <inset date>?
 
 1. No, not even a puff 2. Yes – just a few puffs

- | | |
|--|--|
| | 
3. Yes – 1- 5 cigarettes in total4. Yes – more than 5 cigarettes in total |
|--|--|

Evaluations of likely mechanisms of effect in particular focusing on these strategies that were encouraged and participant perceptions of effect (e.g. participant ratings), including use of EMA/qualitative sub studies.

3 and 6 month survey:

Thinking about the period before you returned to smoking.] We are interested in the extent to which you may have done certain things to help you stay quit.

When you [If M3_SMKSTAT=2: have been/ If M3_SMKSTAT=1: were] strongly tempted to have a cigarette, which of the following [If M3_SMKSTAT=2: have you done/ If M3_SMKSTAT=1: did you do] regularly? (YES/NO)
(YES/NO)

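### Secondary outcome 1c (sustained reduction) is defined in a subset formed after randomisation, the SAP contradicts itself on whether and in whom it is analysed, and its reference consumption is not named

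*SAP*

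**What the plan says.** - **Population.** Under Curtailed Trial Secondary Outcome, item 1c is "at least 50% reduction in cigarettes smoked per day (or week if originally non-daily smoker"), measured "from baseline in those who do not achieve abstinence at 6 months". Appendix 1 repeats the restriction: "Sustained reduction in cigarette smoking at 6 months in those who do not achieve abstinence".
- **Analysis set.** The section Analysis of primary and secondary outcomes says: "All participants will be included in the analysis and will be analysed according to the treatment group to which they were randomised". It counts participants missing at six months as relapsed and as not having reduced.
- **Model.** The same section puts all analyses through a logistic regression on the number of interventions assigned (0, 1 or 2), adjusted for country. The dependent variable it names is relapse status.
- **Feasibility.** Curtailed secondary objective 3 concerns sustained reductions among treatment failures. It offers exploratory EMA and qualitative analyses "complementing reduction reports at follow-ups; quantitative analysis will not be possible in the curtailed trial".
- **Baseline.** The Inclusion Criteria require that participants "are still abstinent at point of recruitment". Curtailed Measures lists, among the baseline smoking measures, a "heaviness of smoking index referenced to when they were smoking". Cigarette consumption is listed for all follow-ups.
- **Data source.** For 1c, Appendix 1 gives one 6-month question, "How many cigarettes do you currently smoke per day (OR per week if nondaily smoker"), and no baseline or 3-month item.

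**The concern.** Abstinence at 6 months is an effect of treatment. If an intervention works, the participants left in the non-abstinent group of an active arm are a different mix from those left under usual care. Comparing reduction rates between these groups mixes any effect on consumption with the selection that the effect on abstinence produced. A helpful programme could look harmful on 1c, or one with no effect on consumption could look helpful.

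The analyst is also left to choose. The definition, the all-participants rule, the general model and objective 3 point to different analyses. If all participants are included, the SAP does not say how abstainers are coded on 1c. That choice should not be made after the data are seen, least of all in a trial whose stated remaining use is to feed later meta-analysis.

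**Working it through.** **1. The SAP's own figures.** No figure is stated for 1c, so the sample size was reproduced to confirm how the SAP uses its relapse rates (Original Sample Size: 70% UC, 58% with one intervention, 48% with both).
- Margins: (70 + 58)/2 = 64% and (58 + 48)/2 = 53%.
- Two proportions, two-sided alpha 0.025, 90% power: 496 per margin; with continuity correction 514, and 514/2 = 257 per arm, as stated.
- With 235/2 = 117.5 per margin, power is 29.7% (stated 30%).
- A trend test with scores 0/1/2 at one-sided 0.05 gives 78.7% (stated 78%).

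The rates are therefore used as the SAP uses them. They are 1-to-12-month rates.

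**2. Size of the 1c subset.** N = 235 allocated 1:1:1:1 gives 235/4 = 58.75 per arm.

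| Arm | Calculation | Non-abstinent |
|---|---|---|
| UC | 58.75 × 0.70 | 41.1 |
| SR | 58.75 × 0.58 | 34.1 |
| S3P | 58.75 × 0.58 | 34.1 |
| SR+S3P | 58.75 × 0.48 | 28.2 |
| Total | | 137.5 |

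This assumes that non-abstinence means the primary definition; 1c does not say. Seven-day point prevalence would give a smaller subset.

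Missing participants enter the subset as not reduced. With assumed missingness of 0, 10, 20, 30 or 40%, the number in the subset with an observed consumption value is 137.5 minus that share of 235: about 137, 114, 90, 67 or 43.

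**3. Can the subset comparison mislead?** Assumed values, not in the SAP: half the participants are light and half heavy smokers; 50% of light and 15% of heavy relapsers cut down by at least half, whatever their arm. Treatment therefore has no effect on consumption after relapse. Proportion reduced among relapsers = (light relapse × 0.50 + heavy relapse × 0.15)/(light relapse + heavy relapse).
- UC, relapse 60% light and 80% heavy (70% overall): (0.30 + 0.12)/1.40 = 30.0%.
- SR+S3P (48% overall), mainly light smokers kept abstinent, relapse 26%/70%: (0.13 + 0.105)/0.96 = 24.5%.
- SR+S3P, mainly heavy smokers kept abstinent, relapse 50%/46%: (0.25 + 0.069)/0.96 = 33.2%.
- SR+S3P, both benefit in proportion: 30.0%.

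**4. Does the coding of abstainers matter?** Same assumed values, UC against the first two SR+S3P cases:

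| Abstainers on 1c | UC | SR+S3P |
|---|---|---|
| Excluded | 30.0% | 24.5% or 33.2% |
| Coded not reduced | 0.70 × 0.300 = 21.0% | 0.235/2 = 11.75% or 0.319/2 = 15.95% |
| Coded reduced | 30 + 21 = 51.0% | 52 + 11.75 = 63.75% or 52 + 15.95 = 67.95% |

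The direction of the difference depends on a coding rule that the SAP does not give.

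**5. Reference and duration.** Current consumption at recruitment is nominally zero by the inclusion criterion, and a percentage reduction from zero is undefined. The word *originally* in the 1c definition and the retrospective smoking index both point to recalled pre-quit smoking. No section says so, and Appendix 1, which exists to give each outcome's data source, names no baseline consumption item for 1c. A single question about current smoking at 6 months gives a level at one time.

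**The case against.** The strongest reply is that no biased test is fixed. Objective 3 rules out quantitative analysis, the analysis section separately promises summary measures of secondary outcomes by arm, and the model is written only for relapse status. On that reading 1c is already descriptive. This stands in part: the biased test is one reading of inconsistent text. But the same section says that all analyses use the model and that all participants are included for secondary outcomes, and nothing says which statement governs.

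The missing-data rule is not evidence against the subset. Participants set to smoking join the non-abstinent group and need a reduction code, so the rule fits the definition of 1c. It conflicts only with objective 3.

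Three stronger readings are tempting and not supported:
- *The outcome is impossible because everyone is abstinent at baseline.* The text itself suggests recalled pre-quit consumption. What can be supported is that the reference and its item are not named.
- *The subset analysis would produce a large spurious harm.* If half of UC relapsers reduce and all 22 points of prevented relapse come from would-be reducers, the figures are 35/70 = 50% against 13/48 = 27%. The arithmetic is right, but this is an extreme assumed case. Milder assumptions give a small distortion in either direction, or none.
- *The word sustained has to go.* Consumption is collected at all follow-ups, so adding the 3-month report is an equally available repair.

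**Conclusion.** The point holds as an internal contradiction plus an incomplete definition. Outcome 1c is conditional on a post-randomisation event, and four parts of the SAP give instructions for it that cannot all be followed. If 1c is put through the general model in non-abstainers, the result is not a randomised comparison. The size and direction of the bias are unknown; the 24.5% to 33.2% range against 30.0% rests wholly on assumed values and shows only that both directions are possible. The subset of about 137 rests on 12-month planning rates applied to a 6-month outcome, equal arm sizes and the primary definition of abstinence.

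The primary outcome, its model and its power are untouched. This should be fixed before the 6-month analysis, but it affects the interpretation of one secondary outcome only.

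**What to change.** 1. State that 1c is reported descriptively by arm among non-abstainers, with no between-arm test, and exclude it from the logistic model. Say which definition of abstinence sets the group.
2. Reconcile curtailed objective 3, outcome 1c, the all-participants statement and the model statement accordingly.
3. If a comparison is wanted, make it in all randomised participants, for example abstinent or at least 50% below pre-quit consumption, with missing counted as not reduced. Note that such a composite can mask a gain in abstinence: in the extreme case above it is 30 + 35 = 65% in UC and 52 + 13 = 65% in SR+S3P, although 22 points more are abstinent with both.
4. Define the reference as pre-quit consumption recalled in the baseline survey and name the item in Appendix 1, after confirming that it was collected.
5. Either add the 3-month consumption report to the definition and to Appendix 1, or drop *sustained*.

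The cost is SAP wording. No extra follow-up is needed if pre-quit consumption was recorded at baseline; the SAP does not show that it was. If it was not, the 50% threshold has no reference and 1c could be reported only as consumption at follow-up.

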All analyses will be conducted using a logistic regression where relapse status is regressed onto an ordinal predictor which codes the number of active interventions assigned (0, 1, or 2) adjusted for the stratified (i.e. country). A likelihood ratio test will be conducted initially to assess whether the ordinal predictor should be modelled as continuous or categorical. If the treatment effect is positive, we will also explore the moderating role of country on the treatment effect by including an interaction term between 'treatment' and country. Estimates and 95% confidence intervals will be presented.

Sensitivity analyses of the primary outcome

To assess the robustness of the results, a series of sensitivity analyses will be conducted using different approaches to impute missing information; specifically, we will use multiple imputation by chained equation [26] and complete case analysis where we exclude cases with missing outcomes. To build the multiple imputation model, we will explore differences in baseline measures between participants with complete and missing outcome measures.

Sensitivity analyses will also explore alternative definition of sustained abstinence for the primary outcome, e.g. Russel standard defined as not smoking more than 5 cigarettes since 2-weeks post quit.

Lastly, per protocol analysis will also be conducted to exclude those participants who were not using their allocated product. This will allow us to assess the robustness of the results following departures from the randomised treatment.

No statistical testing (p -value) will be reported for the sensitivity analyses as we are mostly interested in assessing how robust the results are.

All analyses will be carried out in Stata.

Number needed to treat

The number needed to treat (95%CI) for one additional person not to relapse will also be estimated.

Adverse events

The number of adverse events and serious adverse events by study arm will be presented and specific events will be listed.

Tables to be included

- Descriptive statistics of baseline characteristics by study arm.
- Proportion of missing information on the primary and secondary outcomes by study arm.

- Differences in baseline characteristics between patients with complete vs. missing information on the primary outcome.

Figures to be included

- CONSORT diagram

References

1. Ferguson, J., et al., *The English smoking treatment services: one-year outcomes*. *Addiction*, 2005. **100**(s2): p. 59-69.

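### Secondary outcome 1c is defined only in non-abstainers, while the SAP's general analysis text covers all participants and objective 3 rules out quantitative analysis; any arm contrast fitted to that subset would not be a randomised comparison

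*SAP*

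**What the plan says.** Four parts of the SAP bear on this outcome.

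- **Curtailed Trial Secondary Outcome, item 1c**, measures the reduction "from baseline in those who do not achieve abstinence at 6 months". **Appendix 1** repeats the restriction: "Sustained reduction in cigarette smoking at 6 months in those who do not achieve abstinence".
- **Analysis of primary and secondary outcomes** states: "Analyses for the primary and secondary outcomes will use the intention-to-treat (ITT) approach". It continues: "All participants will be included in the analysis and will be analysed according to the treatment group to which they were randomised". Participants with missing six-month outcomes are taken to have relapsed "and to have not reduced their number of cigarettes smoked per day from baseline".
- The same section then gives the model: "All analyses will be conducted using a logistic regression where relapse status is regressed onto an ordinal predictor". The predictor is the number of interventions assigned (0, 1 or 2), with adjustment for country.
- **Secondary Objectives, Curtailed Trial, objective 3**, asks about reduced consumption among treatment failures. It describes the work as exploratory sub-study analysis "complementing reduction reports at follow-ups; quantitative analysis will not be possible in the curtailed trial".

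The SAP does not say how abstainers are coded for 1c. Nor does it say whether abstinence in 1c means the sustained definition of the primary outcome or the 7-day definition of item 1b.

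**The concern.** Abstinence at 6 months lies downstream of treatment. If an intervention works, the people it keeps from relapsing leave the 1c denominator in the intervention arms, while their counterparts in usual care stay in it. The remaining groups then differ in composition, and randomisation no longer protects the comparison. If those kept abstinent would otherwise have smoked lightly, the intervention looks harmful on reduction. If they would have smoked heavily, it looks helpful. Neither result needs any effect on consumption.

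The missing-data rule adds to this, because every non-responder enters the subset as a failure who has not reduced. The SAP also intends its results for later meta-analysis, so a selection-driven odds ratio could be carried forward as a treatment effect.

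Because the sections disagree, an analyst could fit a model, produce a table or do nothing, and could choose after seeing the data.

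**Working it through.** **1. Are the planning rates usable?** The SAP gives no figure for 1c, so the only relapse rates available are those in Original Sample Size: 70% (usual care), 58% (one intervention) and 48% (both), at 12 months. They reproduce the SAP's own figures:

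- Two-arm averages are (70+58)/2 = 64% and (58+48)/2 = 53%. A two-sided test at 0.025 with 90% power and continuity correction needs 514 per pair of arms, or 257 per arm, as stated.
- With 235 participants, power is 29.7% for a main effect (stated 30%), 50.9% for four arms (stated 51%) and 78.7% for the one-sided trend (stated 78%).

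**2. Size of the subset.** With 235/4 = 58.75 per arm, expected failures are 58.75×0.70 = 41 with no intervention, 117.5×0.58 = 68 with one and 58.75×0.48 = 28 with two. That is about 137 of 235 (58%), drawn from 70% of usual care but 48% of the two-intervention arm. At an assumed 20% loss to follow-up, 0.20×235 = 47 participants, or 47/137 = 34% of the subset, would be non-responders scored as not reduced.

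**3. Spurious contrast, no intervention versus two.** Assumptions, none of them in the SAP:

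- treatment has no effect on consumption;
- treatment causes no one to relapse;
- 40% of usual-care failures reduce by at least half.

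Per 100 randomised, usual care has 70 failures, of whom 28 reduced. The two-intervention arm has 48 failures, because 22 relapses are prevented. If a share s of those 22 would have been reducers, the proportion reduced among failures is (28 − 22s)/48.

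| s | Reduced among failures, two interventions | Usual care | Odds ratio |
|---|---|---|---|
| 0.2 | 23.6/48 = 49.2% | 40% | 1.45 |
| 0.4 | 19.2/48 = 40.0% | 40% | 1.00 |
| 0.6 | 14.8/48 = 30.8% | 40% | 0.67 |
| 0.8 | 10.4/48 = 21.7% | 40% | 0.41 |

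A second calculation fixed separate reduction probabilities for persistent and prevented relapsers. Probabilities of 0.20 and 0.60 gave an odds ratio of 0.52; 0.50 and 0.20 gave 1.46. Equal probabilities gave 1.00.

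**4. Scale of the planned model.** Entered as continuous, the predictor gives an odds ratio per added intervention. For the one-intervention arms, prevented relapses are 12 per 100, so the proportion reduced is (28 − 12s)/58. With 41/68/28 failures, the expected per-step odds ratios are 1.20 (95% CI 0.74 to 1.94) at s = 0.2, 0.82 (0.50 to 1.35) at s = 0.6 and 0.65 (0.39 to 1.10) at s = 0.8.

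**5. Taking all participants literally.** If abstainers are kept in and coded as not reduced, a 30% reduction rate in every relapser gives 0.48×0.30 = 14.4% with two interventions and 0.70×0.30 = 21.0% in usual care, an odds ratio of 0.63. Quitting is then scored as failure.

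**6. Abstinent or at least 50% reduced, over all randomised.** Usual care is 30 + 28 = 58%. Two interventions give 52 + 23.6 = 75.6%, 52 + 14.8 = 66.8% and 52 + 10.4 = 62.4% for s = 0.2, 0.6 and 0.8. The rise is 22(1 − s) points, all of it from abstinence.

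**The case against.** The strongest reply is that the SAP never clearly plans an arm contrast on 1c. The definition and Appendix 1 only describe a measure. The model sentence names relapse status, not reduction. Objective 3 disclaims quantitative analysis, and Descriptive statistics promises summary measures of secondary outcomes by arm, so a purely descriptive 1c is a fair reading. This stands in part. A reader might infer that the SAP definitely commits to a biased comparison, and the text does not support that. But it does not exclude one either: the model is said to cover all analyses, and a missing-data rule specific to reduction has little purpose unless 1c is analysed.

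A reader might also infer that objective 3 itself gets a biased answer. It does not follow. That objective asks about treatment failures by design, and a descriptive proportion answers its first part without this bias.

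Nor can it be said that someone who relapsed early and then quit again would count as a reducer. That holds only if abstinence in 1c means sustained abstinence. Under the 7-day definition in item 1b, that person leaves the denominator.

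The figures are illustrative. They apply 12-month planning rates to a 6-month outcome, rest on assumed reduction rates and show the widest contrast. Per added intervention the distortion is smaller, and every expected interval includes 1. To say that 1c would visibly contradict a true benefit on the primary outcome is more than these numbers show.

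Finally, the composite moves in the direction of the relapse effect by construction, so it answers a different question from reduction among those who smoke. This is correct and limits what the composite can replace.

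**Conclusion.** The point holds conditionally. What is certain is that the 1c denominator, the all-participants statement and the objective 3 disclaimer cannot all stand as written, and that abstinence in 1c is undefined. If the general model is fitted to non-abstainers, the result is not a randomised comparison. With no effect on consumption, the odds ratio for two interventions versus none could lie anywhere from about 0.4 to 1.5 under the assumptions shown. It equals 1.0 only where prevented and persistent relapsers would reduce equally often, and nothing in the SAP supports assuming that. Including abstainers as not reduced does not repair it. The primary outcome is unaffected. This should be settled before analysis, but it concerns one secondary outcome.

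**What to change.** 1. Reconcile objective 3 with item 1c, the general analysis section and Appendix 1, so that the SAP says in one place whether and how reduction is analysed.
2. State whether sustained or 7-day abstinence sets the 1c denominator.
3. Report reduction among non-abstainers as descriptive counts and percentages by arm, with non-responders on a separate line and no treatment-effect estimate or test.
4. If an arm comparison is wanted, define it over all randomised participants as abstinent or at least 50% reduced, counting missing as neither, in the country-adjusted logistic model. Show the two components side by side, and state that the result is partly driven by abstinence and does not isolate an effect on consumption.

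The cost is SAP wording and, if step 4 is taken, one derived variable from survey items already collected. What is given up is a formal test of reduction among smokers, which this subset cannot support as a randomised comparison.
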